5.4. Other Endpoints

Other endpoints collected for the DCD Heart Transplanted Recipient Population include:

- Patient and graft survival at 30 days post-transplant
- Patient and graft survival at 30 days and initial hospital discharge, if later than 30 days
- Severe PGD (left or right ventricle) (not including rejection or cardiac tamponade) according to ISHLT consensus manuscript (as defined in [Appendix 1](#) of this protocol)
- Use of post-transplant mechanical circulatory support (LVAD, RVAD, BiVAD) for > 72 hours immediately post-transplant.

Other endpoints calculated for both the DCD Heart Transplanted Recipients and the SOC Heart Transplanted Recipients (SOC1+SOC2) include:

- Patient survival at 1 year after transplant (collected post-approval); comparison of **DCD Heart Transplanted Recipients** and **SOC Heart Transplant Recipients (SOC1 + SOC2)** through UNOS/OPTN database.

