15. Mancini, D. and Lietz, K. Selection of Cardiac Transplantation Candidates in 2010. *Circulation*; 2010; 122:173-183.

16. Messer, et al. Outcome after Heart Transplantation from Donation after Circulatory-determined Death Donors. *J. Heart. Lung Transplant*; 2017, 36(12):1311-1312.
17. Nicoara, et al. Primary Graft Dysfunction after Heart Transplantation: Incidence, Trends and Associated Risk Factors. *Am. J. Transplant.*; 2018; 18:1461-1470.
18. Peura, et al. on behalf of the American Heart Association Heart Failure and Transplantation Committee, Recommendations for the Use of Mechanical Circulatory Support: Device Strategies and Patient Selection: A Scientific Statement from the American Heart Association. *Circulation*; 2012; 126:2648-2667.
19. Squiers, et al. Application of the International Society for Heart and Lung Transplantation (ISHLT) criteria for Primary Graft Dysfunction after Cardiac Transplantation: Outcomes from a High-Volume Centre. *Euro. J. Cardio-Thoracic Surg*; 2017, 51:263-270.
20. Wilhelm, M.J. Long term outcome following heart transplantation: Current Perspective. *J. Thoracic Dis.*; 2015; 7(3):549-551.

APPENDIX 1. ISHLT CONSENSUS MANUSCRIPT HEART PRIMARY GRAFT DYSFUNCTION (PGD) (KOBASHIGAWA, ET AL., 2014)

Table 6 Definition of Severity Scale for Primary Graft Dysfunction (PGD)

1. PGD-Left ventricle (PGD-LV):	Mild PGD-LV: One of the following criteria must be met:	LVEF \leq 40% by echocardiography, or Hemodynamics with RAP $>$ 15 mm Hg, PCWP $>$ 20 mm Hg, CI $<$ 2.0 L/min/m ² (lasting more than 1 hour) requiring low-dose inotropes
	Moderate PGD-LV: Must meet one criterion from I and another criterion from II:	I. One criteria from the following: Left ventricular ejection fraction \leq 40%, or Hemodynamic compromise with RAP $>$ 15 mm Hg, PCWP $>$ 20 mm Hg, CI $<$ 2.0 L/min/m ² , hypotension with MAP $<$ 70 mm Hg (lasting more than 1 hour) II. One criteria from the following: i. High-dose inotropes—Inotrope score $>$ 10 ^a or ii. Newly placed IABP (regardless of inotropes)
	Severe PGD-LV	Dependence on left or biventricular mechanical support including ECMO, LVAD, BiVAD, or percutaneous LVAD. Excludes requirement for IABP.
2. PGD-right ventricle (PGD-RV):	Diagnosis requires either both i and ii, or iii alone:	i. Hemodynamics with RAP $>$ 15 mm Hg, PCWP $<$ 15 mm Hg, CI $<$ 2.0 L/min/m ² ii. TPG $<$ 15 mm Hg and/or pulmonary artery systolic pressure $<$ 50 mm Hg, or iii. Need for RVAD

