Sensitivity analyses of the primary effectiveness endpoint were not described in the protocol and have been added to the SAP. First, an unadjusted analysis will be performed with the same non-inferiority margin as recommended by the FDA. Additionally, a tipping point analysis will be performed without risk factor adjustment using the Wald method, in which subjects with unsuccessful or missing outcomes in the SOC Heart Transplanted Recipient Population will have successful outcomes imputed iteratively. The primary effectiveness endpoint will also be analyzed using Kaplan Meier methods. Per FDA's request, a sensitivity analysis was added to compare the primary effectiveness by randomization (i.e., to compare the DCD Heart Possible Population vs. the SOC Heart Only Population).

The protocol defines the secondary effectiveness endpoint (DCD donor heart utilization rate) as the number of eligible DCD donor hearts that met the warm ischemic time (WIT) limit ( $\leq 30$  mins) and were instrumented on the OCS Heart System that meet the acceptance criteria for transplantation after OCS Heart preservation divided by the total number of eligible DCD donor hearts that met the warm ischemic time limit above and were instrumented on the OCS Heart System (i.e., based on the OCS Heart Population). It is clarified in the SAP that this is the primary analysis of the secondary effectiveness endpoint. The utilization rate based on the modified OCS (mOCS) Heart Population is added in the SAP, defined as the number of DCD hearts that were successfully transplanted after preservation and assessment on the OCS divided by the total number of DCD donor hearts that were instrumented on the OCS.

The protocol defines post-transplant mechanical circulatory support (MCS) as LVAD, RVAD, and BiVAD. The list of MCS was updated to also include ECMO, TAH, and IABP. For the study endpoint of use of post-transplant MCS for > 72 hours immediately post-transplant, it was clarified that only post-transplant MCS that is initiated within the initial 24 hours (T24 visit) post-OR discharge with an implant duration of greater than 72 hours will be considered to meet this study endpoint. This was proposed to avoid double counting IABP that was inserted pre-transplant and stayed for 1-2 days until the patient clotting factors are stabilized post-transplant.

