### **4.3 Other Endpoints**

Other endpoints collected for the DCD heart transplanted subjects only include:

- Use of post-transplant MCS (including LVAD, RVAD, BiVAD, ECMO, TAH, IABP) for  $> 72$  hours immediately post-transplant (i.e., use initiated within 24 hours after OR discharge).

Other endpoints collected for both the DCD heart transplanted recipients and the SOC heart transplanted recipients (SOC1+SOC2) are as follows:

- Patient and graft survival at 30 days post-transplant.
- Patient and graft survival at 30 days or initial hospital discharge, if later than 30 days.
- ISHLT moderate-severe PGD (left or right ventricle) (not including rejection or cardiac tamponade) within 24 hours according to ISHLT consensus manuscript (as defined in Appendix 1 of the protocol) for both OCS and SOC patients.
- ISHLT Severe PGD (left or right ventricle) (not including rejection or cardiac tamponade) within 24 hours according to ISHLT consensus manuscript (as defined in Appendix 1 of the protocol).
- Patient survival assessed at the 12 months post-transplant follow-up visit.
- Patient and graft survival at 30, 180, and 365 days post-transplant estimated by Kaplan Meier method.

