### **5.3 Handling of Dropouts and Missing Data**

No imputation of missing data for trial subjects will be performed for any effectiveness or safety outcome.

An AE will be considered treatment emergent unless it can be unequivocally determined (from the partial onset date and/or a partial or complete stop date) that the event occurred prior to transplantation.

For duration of ICU stay calculation, the date time of the clinical order of discharge will be used. If the clinical order of discharge date is not available, the actual discharge date will be used. Missing ICU admission time will be imputed as 00:00, and missing ICU discharge time will be imputed as 23:59. If the imputed clinical order of discharge date time is after the actual discharge, the actual discharge date time will be used for calculation.

For duration of post-transplant MCS calculation, missing support start time will be imputed as 00:00, and missing support end time will be imputed as 23:59. If the imputed MCS start time is before the OR discharge, the OR discharge time will be used as the starting point for the duration calculation.

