### 12.3 Other Effectiveness Endpoints Analyses

Other endpoints collected for the DCD and DCD-mITT Heart Transplanted Recipient Populations include:

- Use of post-transplant MCS (includes LVAD, RVAD, BiVAD, ECMO, TAH, or IABP) for > 72 hours immediately post-transplant. To clarify, pre-transplant IABP (regardless of indication) that is removed per standard of care a couple of days post-transplant will be excluded from any post-transplant MCS analysis. The pre-transplant IABP that is maintained during transplantation and restarted for post-transplant cardiac support, and the IABP placed post-transplantation will be considered as newly placed IABP. Only the post-transplant MCS initiated within the initial 24 hours (T24 visit) post-transplant with a duration of use greater than 72 hours will be considered to meet this study endpoint. In cases where a recipient received more than one type of post-transplant support, the support type with the longest continuous duration will be used.

Other endpoints collected for both the DCD heart transplanted recipients and the SOC heart transplanted recipients (SOC1+SOC2) include:

- Patient and graft survival at 30 days post-transplant
- Patient and graft survival at 30 days or initial hospital discharge, if later than 30 days
- Moderate-severe PGD (left or right ventricle) (not including rejection or cardiac tamponade) according to ISHLT consensus manuscript (as defined in Appendix 1 of the protocol) within 24 hours post-transplant
- Severe PGD (left or right ventricle) (not including rejection or cardiac tamponade) according to ISHLT consensus manuscript (as defined in Appendix 1 of the protocol) within 24 hours post-transplant
- Patient survival assessed at the 12 months post-transplant follow-up visit
- Patient and graft survival at 30, 180, and 365 days post-transplant estimated by Kaplan Meier method

Each endpoint, except Kaplan-Meier estimates, will be summarized using counts and percentages and an exact (Clopper-Pearson) 95% confidence interval for the true percentage based on the binomial distribution.

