## 14.0 OTHER ANALYSES

Use of post-transplant MCS (includes LVAD, RVAD, BiVAD, ECMO, TAH, or IABP) will be summarized. Pre-transplant IABP (regardless of indication) that is removed per standard of care a couple of days post-transplant will be excluded from any post-transplant MCS analysis. Pre-transplant IABP that is maintained during transplantation and restarted for post-transplant cardiac support, and the IABP placed post-transplantation will be considered as newly placed IABP. Frequencies and percentages of patients with post-transplant MCS will be summarized overall and by support type. Descriptive statistics for duration of support will be provided for each type. Post-transplant IABP will also be tabulated by indications, including per center specific protocol - prophylactic, for cardiac support (graft dysfunctions not meeting the PGD criteria), and for PGD. IABP and indications will be summarized by CEC adjudication.

Recipient post-transplant ICU stay(s) will be summarized using descriptive statistics for the initial ICU stay duration to clinical order of discharge and the re-admission ICU stay duration from ICU re-admission to clinical order of re-admission discharge, and using frequencies and percentages for whether the recipient was readmitted in the ICU.

Post-transplant hospitalization(s) will be summarized using descriptive statistics for the initial hospital stay duration and the re-hospitalization stay duration and frequencies and percentages for whether the recipient was re-hospitalized.

Primary graft dysfunction surveillance data through 24 hours post-transplant will be summarized using frequencies and percentages for both DCD and SOC groups.

Post-transplant invasive hemodynamics, inotropic support and echocardiogram data will be listed.

The above analyses will be performed for the DCD Heart Transplanted Recipient Population and DCD-mITT Heart Transplanted Recipient Population. The above analyses will be done for the SOC Heart Transplanted Recipient Population and SOC modified Intent-to-Treat (SOC-mITT) Heart Transplanted Recipient Population, only if explicitly stated.

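### As SAP 12.3 is written, unbroken mechanical support above 72 h that passes between two device types can be scored as not meeting the MCS > 72 h endpoint, which is narrower than protocol 5.4 and SAP 4.3

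*SAP*

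**What the plan says.** Protocol 5.4 lists among the other endpoints for DCD recipients: "Use of post-transplant mechanical circulatory support (LVAD, RVAD, BiVAD) for > 72 hours immediately post-transplant". SAP 4.3 keeps this form, adds ECMO, TAH and IABP to the device list, and ties it to "use initiated within 24 hours after OR discharge". Both speak of MCS as a class. Neither has a rule for recipients with several device types.

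SAP 3.5, which records changes from the protocol, says that what counts is "only post-transplant MCS that is initiated within the initial 24 hours (T24 visit) post-OR discharge with an implant duration of greater than 72 hours". It also explains the wider device list and the handling of IABP, but it does not mention a longest-type rule.

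SAP 12.3 restates the criterion ("Only the post-transplant MCS initiated within the initial 24 hours (T24 visit) post-transplant with a duration of use greater than 72 hours") and ends the same bullet with: "In cases where a recipient received more than one type of post-transplant support, the support type with the longest continuous duration will be used".

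SAP 5.3 covers missing start and end times and adds: "If the imputed MCS start time is before the OR discharge, the OR discharge time will be used as the starting point". It does not say how consecutive types are joined. SAP 14.0 adds a separate tabulation: "Frequencies and percentages of patients with post-transplant MCS will be summarized overall and by support type", with durations by type.

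**The concern.** The longest-type sentence stands directly after the 72 h criterion, inside the endpoint bullet. Its natural meaning is that the duration of one type decides whether the endpoint is met. A handover from one device type to another then splits a single period of support into two shorter ones, and neither may pass 72 h. A recipient supported without a break for 110 h can be reported as not having had more than 72 h of MCS, while a recipient with 73 h on one device is counted.

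The stake is how prolonged support in DCD recipients is described, and whether two programmers working from different SAP sections would report the same count. The primary, secondary and safety endpoints are not derived from this rule.

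**Working it through.** The plan gives no rate, sample size or power for this endpoint, so there is no figure to reproduce. The check applies the stated rules to support histories.

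**Inputs.** Threshold: more than 72 h (protocol 5.4; SAP 4.3, 12.3). Start window: within 24 h (SAP 3.5, 4.3, 12.3). Several types: longest single type (SAP 12.3). Planned DCD recipients: 90 (protocol 10.5, SAP 3.4). The histories are illustrations, in hours from OR discharge.

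**Range missed.** Let two back-to-back types last d1 and d2 hours. SAP 12.3 scores the recipient as not met if max(d1, d2) ≤ 72. Unbroken support exceeds the threshold if d1 + d2 > 72. Both hold for totals above 72 h and up to 72 + 72 = 144 h.

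**Example.** ECMO 0-48 h gives d1 = 48; RVAD 48-110 h gives d2 = 110 − 48 = 62. The longest type is 62 h, so the endpoint is not met. The joined total is 48 + 62 = 110 h, so as a class it is met.

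**Grid.** Take whole-hour starts from 0 to 24 (25 values) and d1, d2 from 1 to 72 with d1 + d2 > 72. There are 72 × 72 = 5,184 pairs, of which 2,556 have a sum of 72 or less. That leaves 2,628 pairs, and 25 × 2,628 = 65,700 patterns, with totals of 73 to 144 h. Judged one type at a time, none is met, whichever of the 24 h and longest-type rules is applied first. Judged as a class, all 65,700 are met.

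**Further histories.** Column A requires one type to satisfy both conditions, with the 24 h filter first. B is the same with the longest type chosen first. C puts the 24 h limit on MCS use overall and then tests the longest type. D joins support across types.

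| History (hours) | A | B | C | D |
|---|---|---|---|---|
| ECMO 0-48, RVAD 48-110 | No | No | No | Yes |
| ECMO 0-72, RVAD 72-144 | No | No | No | Yes |
| ECMO 0-30, LVAD 30-240 | No | No | Yes | Yes |
| IABP 0-80 with ECMO 30-130 | Yes | No | Yes | Yes |
| IABP 0-10, gap, ECMO 60-160 | No | No | Yes | No |

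Rows 1 and 2 are the main point. Rows 3 to 5 show secondary ambiguities: whether one type must meet both conditions, and in which order the rules apply. The origin of the 24 h window also differs: OR discharge in SAP 3.5 and 4.3, post-transplant in SAP 12.3.

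**Size.** One recipient in 90 is 1/90 = 1.1 percentage points; two are 2.2 and three are 3.3. With assumed counts, 11/90 = 12.2% (exact 95% CI 6.3-20.8%) would be reported as 10/90 = 11.1% (5.5-19.5%) if one recipient were missed.

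**The case against.** **The rule is explicit.** The longest single type is a definable choice for a descriptive endpoint, and nothing in the documents requires adding across devices. This stands as far as it goes. But SAP 12.3 implements an endpoint that SAP 4.3 and the protocol word as a class, and SAP 3.5 does not list the longest-type rule as a change.

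**The sentence may only select which type to report.** This is possible but weaker, because tabulation by type is handled separately in SAP 14.0.

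**These recipients appear elsewhere.** This largely stands. SAP 14.0 counts them as having MCS and gives durations by type. Protocol 8.4.4 lists use of mechanical support among the anticipated SAEs, which are collected to Day 30. Severe PGD will often capture cases that begin with ECMO. It need not capture IABP 0-48 h followed by ECMO 48-110 h: the severe left-ventricular grade in protocol Appendix 1 "Excludes requirement for IABP", and the ECMO starts after the 24 h PGD window of SAP 4.3. That case could still be graded moderate. What is lost is one classification, not the event.

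**A joining rule might exist out of sight.** The table shells and draft case report forms have no content in the copy reviewed, so a derivation note there cannot be excluded. Recording matters too. An RVAD added to a running LVAD gives LVAD 0-40 h then BiVAD 40-100 h if entered as a new type (not met), but LVAD 0-100 h plus RVAD 40-100 h if entered as two devices (met).

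**Stronger readings.** A reader might infer that such a recipient is scored as not met however the plan is read. The documents do not support that: the class wording in protocol 5.4 and SAP 4.3 would count the recipient. A reader might also infer that the published rate must be too low. That fails as well: no handover frequency is given, and under column C a recipient with a gap in support can be counted.

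**Conclusion.** The point holds as an inconsistency. As SAP 12.3 is written, unbroken two-type support of more than 72 h and up to 144 h, with neither type above 72 h, is not counted; protocol 5.4 and SAP 4.3, read as they stand, would count it. This rests on the longest-type sentence deciding the endpoint, and on no joining rule existing in material that is not shown.

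The severity is minor. The endpoint is summarised by counts, percentages and an exact interval in DCD recipients only, with no hypothesis test. The effect is 1.1 percentage points per affected recipient at n = 90. The interval illustration uses assumed counts and is not an estimate. Rule order, time origin and BiVAD recording are separate clarifications and do not add weight to the main point.

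**What to change.** In a dated SAP change before database lock, derive the endpoint from consecutive or overlapping eligible post-transplant support of any type, joined into one period. Count it as met if the joined support starts within 24 h of one stated origin, used alike in SAP 3.5, 4.3 and 12.3, and continues unbroken for more than 72 h. Fix the maximum exchange gap in advance and keep the existing exclusion of pre-transplant IABP.

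Show the single-type version beside it as supportive, stating whether one type must meet both conditions and which rule is applied first. If the sponsor prefers to keep the single-type rule, state those same points and footnote the number of recipients with more than 72 h of unbroken support across types who were scored as not met.

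The cost is SAP wording, one derivation from start and end times that SAP 5.3 already uses, and one extra table row. The downside is that a gap rule must be chosen after enrolment in an open-label study, and the reported rate may be slightly higher. Keeping the single-type version visible lets a reader see what the change does.

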4.1. Trial Design

A prospective, randomized and concurrent controlled, non-inferiority pivotal trial in which subjects who receive a DCD donor heart transplant will be compared to subjects who receive a standard

criteria donor heart transplant (SOC1 and SOC2 - from both randomized and concurrent control groups), adjusting for differences in risk factors. The trial design is illustrated in [Figure 8](#) below.

Figure 8: OCS Heart DCD Heart Trial Design

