## 3.0 STUDY DESIGN

### 3.1 Overview

This is a prospective, randomized and concurrent controlled, non-inferiority pivotal trial in which subjects who receive a DCD donor heart transplant will be compared to subjects who receive a standard of care (SOC) donor heart transplant, regardless of whether those subjects were randomized to receive an SOC donor heart (SOC1) or to potentially receive a DCD donor heart (SOC2). The primary effectiveness comparison between these groups is analyzed by actual treatment and includes adjustment for differences in risk factors. The trial design is illustrated in Figure 1 below.

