### 3.2 Method of Assigning Subjects to Treatment

Primary heart transplant candidates will be screened for trial eligibility. Every eligible candidate will be asked to participate. Consented subjects will be randomized into two groups: ***DCD Heart Possible*** and ***SOC Heart Only***.

Subjects who are randomized into the ***SOC Heart Only*** group will have no possibility for a DCD Heart transplant. Subjects randomized into the ***DCD Heart Possible*** group have the possibility of receiving either a DCD heart or an SOC donor heart, depending upon the donor match. In order to obtain enough subjects with DCD donor heart transplants, subjects will be randomized 3:1 to the ***DCD Heart Possible*** and ***SOC Heart Only*** arms, respectively. Eligible subjects in the ***SOC Heart Only*** group who are transplanted will form one ***SOC Heart Transplanted Recipient group (SOC1)***. In the ***DCD Heart Possible*** arm, if a screened and eligible subject is matched with an SOC donor heart before an eligible DCD donor heart becomes available and is transplanted, these subjects will form a second ***SOC Heart Transplanted Recipient group (SOC2)***.

Note: After completing enrollment there were 6 cases in which a SOC donor heart was transplanted without randomization. These subjects' data will be included in data listings and in ad-hoc analyses to support the final clinical study report.

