### **5.2 Adjustments for Covariates**

The analysis of the primary effectiveness endpoint will be performed using a linear probability model with terms for treatment and the known donor and recipient risk factors for mortality listed in Section 12.1.

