Kaplan-Meier estimates for patient survival and graft survival (graft failure includes heart re-transplant and cardiac graft-related death) probabilities will be calculated for the SOC Heart Transplanted Recipient Population, the SOC-mITT Heart Transplanted Recipient Population, the DCD Heart Transplanted Recipient Population, and the DCD-mITT Heart Transplanted Recipient Population for the following time points: Day 30, Month 6, and Month 12. Of note, the Kaplan-Meier estimates will consider time as a continuous variable measured in days. The Month 6 and Month 12 timepoints will be considered to be 180 and 365 days post-transplantation, respectively. Re-transplanted patients will be censored at the day of re-transplantation. The estimated difference in survival probability (SOC – DCD) and its 90% confidence interval will also be presented at each of the three time points.

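### The 12-month DCD-versus-SOC survival difference is planned only without risk adjustment, so it is open to confounding and is not like for like with the adjusted 6-month primary result

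*SAP*

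**What the plan says.** **How the groups are formed.** SAP 3.1: "The primary effectiveness comparison between these groups is analyzed by actual treatment and includes adjustment for differences in risk factors". In the DCD Heart Possible arm, SAP 3.2 places a recipient in the SOC2 control group "if a screened and eligible subject is matched with an SOC donor heart before an eligible DCD donor heart becomes available". The heart received is thus settled by a donor match after randomization.

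**Where adjustment is planned.** Protocol 4.1 describes the DCD-versus-SOC comparison, with SOC recipients taken "from both randomized and concurrent control groups), adjusting for differences in risk factors". The SAP attaches covariates to the 6-month endpoint: "The analysis of the primary effectiveness endpoint will be performed using a linear probability model with terms for treatment" (SAP 5.2, with the risk factors in 12.1).

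**What is planned at the other times.** SAP 12.3 gives Kaplan-Meier estimates "for the following time points: Day 30, Month 6, and Month 12", and then: "The estimated difference in survival probability (SOC – DCD) and its 90% confidence interval will also be presented". It states no covariates, weights or stratification. The visit-based survival endpoints, including 12 months, are summarized within each group: "Each endpoint, except Kaplan-Meier estimates, will be summarized using counts and percentages and an exact (Clopper-Pearson) 95% confidence interval".

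**Status of the 12-month result.** Protocol 5.4 lists one-year survival among the other endpoints, as a comparison of DCD with SOC1 + SOC2. Protocol 10.3.2 plans it as a summary in both populations. SAP 5.4 provides a separate Month 12 data cut for submission.

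**The concern.** DCD versus SOC1 + SOC2 is not a randomized contrast, because membership of the DCD and SOC2 groups depends on which match came first. The two groups can differ in recipient and donor risk. The plan allows for this at 6 months by modelling the listed risk factors. Differences in recipient risk, such as mechanical support before transplant, do not stop mattering after 6 months, yet the same groups are compared at 12 months without those factors.

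At stake is how the longest comparative survival result is read. A reader who sets the adjusted 6-month difference beside the unadjusted 12-month one may see a change and call it a late effect, when part of it comes from leaving the covariates out. If SOC recipients carry more risk, the unadjusted result flatters DCD. If they carry less, it penalizes DCD.

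**Working it through.** **Step 1. Lay out the planned analyses.** Sources: SAP 3.5, 5.2, 12.1, 12.3 and the list of tables.

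| Comparison | Day 30 | Month 6 | Month 12 |
|---|---|---|---|
| DCD vs SOC, risk-adjusted | none | primary analysis | none |
| DCD vs SOC, unadjusted | Kaplan-Meier difference; group percentages | primary model repeated without covariates; Kaplan-Meier difference | Kaplan-Meier difference; group percentages |
| By randomized arm | none | sensitivity analysis (Tables 2.1.3.1, 2.1.3.2) | none |

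The table shells are not in the available text, so this rests on the SAP sections and the table titles.

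**Step 2. Reproduce the plan's own figure.** Inputs from SAP 3.4: SOC 93%, DCD 85%, margin 20 points, one-sided alpha 0.05, power 80%.

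- Variance term: 0.93 × 0.07 + 0.85 × 0.15 = 0.1926. Distance from the margin: 0.20 − 0.08 = 0.12.
- Unpooled: n = 0.1926 × (1.645 + 0.842)² / 0.12² = 82.7, so 83 per group.
- With the null variance pooled at 0.89: 83.6, so 84, as stated.
- Unpooled power is 80.5% at 84 per group and 82.9% at 90.

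This figure is not in dispute. It fixes the inputs for the precision scale.

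**Step 3. Precision at 90 per group.** 90% CI half-width = 1.645 × √(0.1926/90) = 7.6 points. With 12-month survival assumed to be 88% and 86%, the figures in the UK cohort described in Protocol 2.3.1, it is 1.645 × √((0.88 × 0.12 + 0.86 × 0.14)/90) = 8.2 points.

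**Step 4. Size of the possible bias.** For one binary risk factor that lowers survival by r, with prevalence q in each group:

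expected unadjusted (SOC − DCD) = true difference − (q_SOC − q_DCD) × r

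The documents give neither an imbalance nor an effect size, so these are assumed ranges:

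| Prevalence gap | r = 5 points | r = 10 points | r = 15 points |
|---|---|---|---|
| 10 points | 0.5 | 1.0 | 1.5 |
| 20 points | 1.0 | 2.0 | 3.0 |
| 30 points | 1.5 | 3.0 | 4.5 |

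The shift is 0.5 to 4.5 points, or 7% to 59% of the 7.6-point half-width. Its sign follows the sign of the gap. With a true difference of 8 points and r = 10, a 30-point gap gives 8 − 3 = 5 points if SOC carries more of the factor and 8 + 3 = 11 if DCD does.

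**Step 5. Check by simulation.** Settings: 90 per group, SOC survival 93%, true difference 8 points, r = 10 points, and a least-squares linear probability model with and without the factor (20,000 trials unadjusted, 3,000 of them fitted with adjustment).

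| Prevalence SOC / DCD | Mean unadjusted | Mean adjusted |
|---|---|---|
| 50% / 50% | 8.0 | 7.8 |
| 50% / 40% | 7.0 | 7.9 |
| 50% / 30% | 6.0 | 8.1 |
| 60% / 30% | 5.0 | 7.8 |

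The unadjusted mean moves as the formula predicts, and the adjusted mean stays near 8. Standard deviations are nearly equal (4.4 to 4.6 unadjusted, 4.5 to 4.6 adjusted), so adjusting for one factor costs almost no precision here.

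**The case against.** **There is a like-for-like 6-month result.** The Kaplan-Meier difference is planned at Month 6 as well as Month 12, and SAP 12.1 repeats the primary analysis without covariates. A reader might infer that the 12-month result cannot be compared with any 6-month result. The documents do not support that: the unadjusted series is consistent, and adjusted against unadjusted at 6 months shows what the covariates do. This stands. It does not remove confounding at Month 12, where the unadjusted estimate is the only one.

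**No imbalance is shown.** A reader might infer that the 12-month result is in fact confounded. The documents contain no baseline data and do not indicate a direction. Baseline tables by group (such as 1.4.1 and 1.6.1) will show any imbalance. The supportable wording is that the result is open to confounding.

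**These are other endpoints, without a hypothesis or margin.** This stands. It would be wrong to count how often a 12-month interval clears 0.20, because SAP 3.4 and 12.1 set that margin for 6 months only.

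**Adjustment is imperfect.** This also stands, and it shapes the fix.

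- Per-protocol DCD donors are aged 18 to 49 (Protocol 6.1), so donor age of 55 or more cannot occur among them.
- Ischemic time of 4 hours or more is tied to the preservation method, so adjusting for it may remove part of the treatment effect.
- Without imputation (SAP 5.3), a binary 12-month model drops subjects with no 12-month outcome. The Month 12 cut is timed on DCD completion (SAP 5.4), so some SOC follow-up may be censored.
- Covariates are not the only difference from the primary analysis. Kaplan-Meier uses 180 and 365 days and censors at re-transplantation, whereas the primary uses the nominal visit.
- At Day 30, if survival is about 95%, as in the extended-criteria trial in Protocol 2.4, 180 recipients give about 180 × 0.05 = 9 deaths for a model with treatment and six risk factors.

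**Conclusion.** The point holds in a limited form. SAP 12.3 plans the 12-month SOC − DCD difference only without adjustment, for groups formed by heart received, and plans no estimate by randomized arm at that time. The result is open to confounding of unknown direction. Its size is about 0.5 to 4.5 points under the assumed gaps and effects, which is smaller than the half-width of the interval but not negligible beside a planned difference of 8.

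The unadjusted 12-month result should be read against the unadjusted 6-month results, not against the adjusted primary. A reader might infer that the non-inferiority conclusion is weakened. It is not: the primary analysis is adjusted, has its own unadjusted and by-randomization sensitivity analyses, and does not use the 12-month data. This is a worthwhile low-cost improvement, not a flaw in the primary analysis.

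**What to change.** In SAP 12.3:

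1. Add a supportive risk-adjusted SOC − DCD difference in 12-month survival with a 90% CI, for the DCD/SOC and the DCD-mITT/SOC-mITT sets, shown beside the Kaplan-Meier difference.
2. Use the risk factors of the primary model. If the identity-link fit fails, use least squares with robust standard errors.
3. Repeat the estimate without ischemic time.
4. If 12-month outcomes are censored, use a method that keeps those subjects, such as covariate-weighted Kaplan-Meier or pseudo-values.
5. State that adjusted 12-month results are read against adjusted 6-month results, and unadjusted against unadjusted: Kaplan-Meier with Kaplan-Meier, visit-based with visit-based.
6. Treat adjustment at Day 30 as optional, because few deaths are expected.

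The cost is some SAP wording, limited programming and a few table rows. The primary model already needs these covariates, so no new patients or data are required. Sample size, power and alpha do not change. The limit is residual confounding: donor age of 55 or more cannot be balanced against per-protocol DCD donors, and unlisted factors stay unadjusted. The text should say so.
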